6.2.3 Adjustments for Covariates

Efficacy models with continuous variables based on SBP as the response variable (e.g. change from baseline in office-measured SBP, mean daytime SBP) will have the corresponding baseline value as a continuous covariate.

Similarly, models based on DBP will include the corresponding baseline DBP value as a continuous covariate.

6.2.4 Multiple Comparisons/Multiplicity

Given the preliminary nature of this study, no adjustment for multiplicity will be implemented.

6.2.5 Subgroups

Prespecified subgroup analyses will be conducted for the following subgroups defined at baseline:

- Sex (Male, Female)
- Age (<65, 65-79, 80+)
- Race (African-American vs Non)

- BMI (<25, 25-30, >30 kg/m²)
- Seated SBP (low tertile, middle tertile, high tertile)
- PRA level at Randomization (1 – 5, > 5 ng/mL/h) [Part 2 only]
- Number of concomitant antihypertensive medications at baseline (2 vs 3 or more)
- Use of Thiazide diuretics (yes/no)
- Use of ACEi/ARB (yes/no)

6.2.6 Missing, Unused, and Spurious Data

Unless stated otherwise, missing data will not be replaced with imputed values. When relevant, sections below will address how missing data will be handled for the particular analyses.

Partial dates are allowed on the CRF for adverse events and concomitant medications. Only the day may be entered as unknown for the Adverse Event form while month and day may be entered as unknown for the Concomitant Medications (CM) form. Dates from these forms will be reported in listings as collected. Every effort will be made to query missing dates.

AEs will be flagged as on-treatment treatment emergent AEs (TEAEs) if the CRF question “Did this AE start prior to Randomization?” on the AE form is “No” regardless of whether or not the AE onset date is complete. AEs that cannot be definitively determined as occurring prior to study drug administration will be counted as TEAEs unless either the partial start date or a partial or complete end date indicates the AE as occurring prior to treatment. Partial dates entered in the AE form will be imputed for the purposes of determining whether the record is a treatment emergent adverse event or not based on the following:

- AE onset dates with missing day and non-missing month will be assumed to occur on the first day of the non-missing month, except for AEs occurring in the month and year of first dosing of study drug (including placebo run-in period), in which case the date will be imputed using the date of first dosing of study drug.
- AE onset dates with missing day and month will be assumed to occur on the first day of the non-missing year (i.e., January 1), except for AEs occurring in the year of first dosing of the study drug (including placebo run-in period), in which case the date will be imputed using the date of the first dosing of study drug.
- Partial or missing AE resolution dates will not be imputed.

Partial dates entered in the CM form will be imputed for the purposes of determining whether the record is a concomitant or prior medication based on the following:

- Medications that are not ongoing and have a medication stop date with a missing day and non-missing month will be assumed to occur on the last day of the non-missing month.
- Medications that are not ongoing and have a medication stop date with missing day and month will be assumed to occur on the last day of the non-missing year (i.e., December 31).
- Partial or missing CM start dates will not be imputed.

6.3 Study Population

6.3.1 Subject Disposition

A summary of subjects in the Pre-Screened Analysis Set will display the numbers (and percentages of the population) of:

- Pre-Screened. All subjects who signed the pre-screening informed consent/assent.
- Pre-screen failures
- Reason for pre-screen failure
- Screened. All subjects who signed the main study informed consent/assent
- Main study screen failures.
- Reason for main study screen failure

The following categories will be tabulated in the disposition table among all Pre-Screened subjects as the starting population:

- Number pre-screened
 - Reason for pre-screen failure
- Number screened
 - Reason for screen failure
- Number entering Placebo Run-In
 - Number completing Placebo Run-In
 - Reason for not completing Placebo Run-In
- Randomized
- Analysis Sets
 - FAS
 - Safety Analysis Set
 - PPS
 - PK/PD Analysis Set
- Completed the study treatment. Categories: Yes, No.
- Reason for treatment discontinuation. Categories:
 - Adverse Event
 - Physician Decision
 - Pregnancy
 - Study Terminated by Sponsor
 - Subject Non-Compliance/Protocol Violation(s)
 - Withdrawal of Consent
 - Other
- Completed the study.
 - Categories: Yes, No.
 - Duration (weeks) in the study
- Reason for study discontinuation. Categories:

- Adverse Event
- Death
- Lost to Follow-Up
- Physician Decision
- Pregnancy
- Study Terminated by Sponsor
- Subject Non-Compliance / Protocol Violation(s)
- Withdrawal of Consent
- Other

- Was early discontinuation impacted by COVID-19? Categories: Yes, No.

Protocol deviations will be summarized by treatment group. An additional summary will present the protocol deviations leading to exclusion from PPS.

The disposition and population inclusion data mentioned above will be listed for all subjects. The reasons for being excluded from the PPS will also be provided in the listings.

6.3.2 Demographic and Baseline Characteristics

Subject characteristics defined below will be presented in summary tables and data listings for subjects in the FAS and PP Analysis Sets. No statistical comparisons will be performed.

Demography

- Age (years): Age at time of consent, calculated as the difference between birth year and the year of main study informed consent date.
- Age (categories): <65, 65-79, 80+
- Sex: Male, Female
- Race: American Indian or Alaska Native, Asian, Black or African American, Native Hawaiian or Other Pacific Islander, White, Not Reported, Multiple Races.
- Ethnicity: Hispanic or Latino, Not Hispanic or Latino, Not reported.

Baseline Characteristics assessed at Randomization

- Height (cm)
- Weight (kg)
- BMI (kg/m²)
- BMI Categories: <25, 25-30, >30 kg/m²
- Seated AOBP SBP (mmHg)
- Seated AOBP SBP Category (\leq 160 mmHg, > 160 mmHg)
- Seated AOBP DBP (mmHg)
- Standing AOBP SBP and DBP (mmHg)
- For women, of childbearing potential, post-menopausal, Premenarchal, Sterilized)

Cardiovascular History

- Family history of hypertension (Yes, No)
- Obesity (Yes, No)
- Dyslipidemia (Yes, No)
- Diabetes mellitus (Yes [overall and by type], No)
- History of heart failure (Yes [overall and by NYHA classification], No)
- Number of hospitalizations in past year of cardiovascular reasons (*only for subjects who answered "Yes" to history of heart failure*)
- Previous history of carotid artery disease (Yes, No)
- Previous history of myocardial infarction (Yes, No)
- Previous history of Coronary Artery Bypass Graft (CABG) (Yes, No)
- Previous history of Percutaneous Coronary Intervention (PCI) (Yes, No)
- Previous history of atrial fibrillation (Yes [overall and by arterial fibrillation type], No)
- Previous history of stroke or Transitory Ischemic Attack (TIA) (Yes, No)
- Previous history of peripheral vascular disease (Yes, No)
- Previous history of any other arrhythmias (Yes, No)
- Number of AHT meds
 - Categories: 2, 3 or more
 - Use of Thiazide Diuretics (Yes, No)
 - Use of ACEi/ARB (Yes, No)

Lifestyle

- Smoking Status (Current, Former, Never)
- History of alcohol abuse (Yes, No)
- History of illicit drug use (Yes, No)
- History of any other tobacco use (Yes, No)
- Sedentarism (Yes, No)
- Following 2016 NY Heart Association Guidelines (Yes, No)

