## 1. SYNOPSIS

Name of Sponsor/Company: Mineralflys Therapeutics, Inc.	
Name of Investigational Product: MLS-101: [REDACTED] [REDACTED]	
Name of Active Ingredient: MLS-101	
Title of Study: A Randomized, Double-blind, Placebo-controlled, Dose-ranging, Multicenter Phase 2 Study to Evaluate the Safety, Efficacy, and Tolerability of MLS-101 in Subjects With Uncontrolled Hypertension	
Number of Study Center(s): Approximately 50 centers in the United States for Part 1 and approximately 10 centers in the United States for Part 2	
Study Period: Date first subject enrolled: 30 July 2021 Estimated date last subject last visit: Q3 2022	Phase of Development: Phase 2
Objectives and Endpoints: Objectives: Primary: 

To characterize the effect of MLS-101 on blood pressure (BP) at 5 dosing regimens versus placebo when administered orally for the treatment of uncontrolled hypertension as add-on therapy to stable background treatment

 Secondary: 

To investigate the safety and tolerability of MLS-101 at 5 dosing regimens versus placebo when administered orally for the treatment of uncontrolled hypertension as add-on therapy to stable background treatment

To investigate the pharmacokinetic (PK) profile of MLS-101 at 5 dosing regimens when administered orally for the treatment of uncontrolled hypertension as add-on therapy to stable background treatment

To investigate the pharmacodynamic (PD) parameters of MLS-101 at 5 dosing regimens when administered orally for the treatment of uncontrolled hypertension as add-on therapy to stable background treatment

 Endpoints: Efficacy Primary: 

Change in office-measured (average of last 2 of 5 unattended measurements using an automated oscillometric sphygmomanometer device after approximately 5 minutes of rest in the seated position) systolic blood pressure (SBP) from baseline to the end of Study Week 8 (ie, Study Day <math>56 \pm 2</math> or end-of-treatment period)

 Secondary: 

Change in 24-hour ambulatory blood pressure monitoring (ABPM) parameters (systolic and diastolic) from baseline to the end of Study Week 7 (ie, Study Day <math>49 \pm 2</math>)

	

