## **10.5. Confidentiality**

The investigator must ensure that the subject's confidentiality is maintained for documents submitted to the sponsor, including the following:

- Subjects are to be identified by a unique subject identification number.
- Where permitted, date of birth is to be documented and formatted in accordance with local laws and regulations.
- On the eCRF demographics page, in addition to the unique subject identification number, the subject's age at time of enrollment is to be included.
- For SAEs reported to the sponsor, any source documentation provided (eg, medical records, laboratory results) must have any subject identifier (eg, subject name, initials, medical records number) fully redacted (ie, blacked out) prior to transmission.
- Documents that are not submitted to the sponsor (eg, signed ICFs) are to be kept in confidence by the investigator, except as described below.

In compliance with the CFR/ ICH GCP Guidelines, it is required that the investigator and institution permit authorized representatives of the company, of the regulatory agency(s), and the IRB/IEC direct access to review the subject's original medical records for verification of study related procedures and data. Direct access includes examining, analyzing, verifying, and reproducing any records and reports that are important to the evaluation of the study. The investigator is obligated to inform and obtain the consent of the subject to permit such individuals to have access to his/her study related records, including personal information.

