6.4.1.6 Subgroup Analyses for Primary Efficacy

The change in office-measured SBP from baseline at Study Week 8 in Part 1, along with corresponding 90% confidence intervals will be calculated by treatment group for each of the subgroups of the FAS defined in Section 6.2.5 for both the primary Estimand described in Section 6.4.1.1 and the supplemental Estimand described in Section 6.4.1.5. These results will be considered exploratory.

Subgroup analyses will not be performed for Part 2, due to the small sample sizes, though the primary efficacy endpoint in Part 2 will be summarized by subgroup.

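### Age at consent is derived as consent year minus birth year, which exceeds completed age by one year for about half the subjects and moves a few 64-year-olds into the 65-79 category

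*SAP*

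**What the plan says.** SAP 6.3.2 (Demographic and Baseline Characteristics) labels the variable as age when consent was given and defines it as "calculated as the difference between birth year and the year of main study informed consent date". Day and month of birth are not used. The same section groups the result as under 65, 65 to 79, and 80 and over, and SAP 6.2.5 uses these groups as a prespecified subgroup.

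The subgroup enters three places:
- the Part 1 primary endpoint under both estimands (SAP 6.4.1.6), with the caveat "These results will be considered exploratory";
- the by-week SBP analysis (SAP 6.4.2.2);
- the by-week DBP analysis (SAP 6.4.2.3).

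Protocol 10.5 (Confidentiality) says of the eCRF demographics page that "the subject's age at time of enrollment is to be included". On birth dates it says: "Where permitted, date of birth is to be documented and formatted in accordance with local laws and regulations". The SAP does not mention the eCRF age and gives no reason for working from years.

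**The concern.** The formula does not deliver what its label promises. Take a subject born in November 1956 who consents in August 2021. The year difference is 65, but the subject is 64 and belongs in the lowest category. Measured against completed years the error is 0 or +1 and never negative, so it does not cancel across subjects.

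At stake are the age line of the baseline table and the membership of the age subgroups at the 65 and 80 cut points. If the eCRF age is held in completed years, the database would also carry two ages that disagree for about half the subjects.

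**Working it through.** The documents state no figure on this point, so there is none to reproduce.

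**Inputs from the documents**
- Derivation rule and age categories: SAP 6.3.2 and 6.2.5.
- Planned size: about 160 in Part 1 and 36 in Part 2 (Protocol synopsis).
- Start: "Date first subject enrolled: 30 July 2021" (Protocol synopsis).
- End of Part 1: July 2022 (heading of SAP 2.5.2). Last visit: Q3 2022 (Protocol synopsis). Amendment 5, which added Part 2: 17 February 2022.

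**Assumptions, not in the documents**
- Birthdays are uniform over the year, and consents are uniform within each window.
- Part 1 consents run from 16 July 2021 (first enrollment minus 14 days) to 24 April 2022 (31 July 2022 minus 98 days).
- Part 2 consents run from 17 February 2022 to 8 July 2022 (30 September 2022 minus 84 days).
- Age distribution: either 1% to 4% of subjects are truly 64 at consent, or ages are normal with mean 55 to 65 and SD 9 to 11.

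**Step 1: share one year too high.** The error is 1 if the birthday falls after the consent date in the consent year, and 0 otherwise. For one consent date the expected share is (days left in the year)/365. Averaged over consent dates:

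| Consents | Share overstated |
|---|---|
| Full calendar year | 49.9% |
| Part 1 window | 47.7% |
| Part 2 window | 67.5% |
| Both parts: (160 × 0.477 + 36 × 0.675)/196 | 51.3% |

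So about half holds for the trial as a whole, while Part 2 alone is nearer two thirds.

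**Step 2: mean age.** The error is 0 or 1, so its mean equals the share: about +0.5 year relative to completed years. Exact age gives a different answer. Year difference minus exact age equals the birthday's fraction of the year minus the consent date's fraction. The mean consent fraction is 1 − 0.477 = 0.523 in Part 1 and 1 − 0.675 = 0.325 in Part 2. The mean difference is then 0.5 − 0.523 = −0.02 year in Part 1, 0.5 − 0.325 = +0.18 in Part 2, and about +0.01 overall.

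**Step 3: subjects crossing 65.** Expected number = N × (proportion aged 64) × (share overstated).
- With 1% to 4% aged 64: 160 × 0.01 × 0.5 = 0.8, up to 160 × 0.04 × 0.5 = 3.2.
- With normal ages, the moved share is 0.5 × [F(65) − F(64)]. At mean 55, SD 9 it is 0.5 × 0.0254 = 1.3%, or 2.0 of 160. At mean 65, SD 9 it is 0.5 × 0.0442 = 2.2%, or 3.5 of 160.

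Taken together, this is roughly 1 to 4 of 160.

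**Step 4: subjects crossing 80.** By the same formula, 0.5 × [F(80) − F(79)] runs from about 0.1% to 0.8% over the assumed normal distributions, or about one subject of 160 at most.

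**Step 5: reach.** The primary MMRM (SAP 6.4.1.2) contains treatment, week, their interaction and baseline SBP, with no age term. Age enters only through the baseline table and the subgroups.

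**The case against.** The strongest reply is that the rule may be deliberate. Date of birth is collected only where permitted, and the SAP revision, which lists clarifications found during programming, still works from birth year. That would fit a database holding birth year only. This stands as a possibility, but the SAP does not say so, and Protocol 10.5 separately requires an age on the eCRF.

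A reader might infer that the eCRF therefore holds the true age and that the SAP discards a correct value for a worse one. The documents do not support that. Protocol 10.5 is a confidentiality section, it does not say how the age field is filled, and the eCRF is not available. The field could itself come from birth year.

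A reader might also infer that reported mean age is biased in an absolute sense. It is not. Completed years truncate, and against exact age the year difference is nearly unbiased overall (step 2). The +0.5 year exists only relative to completed years, which is the natural reading of an age at consent cut at 65 and 80.

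Finally, the rule uses only quantities fixed before randomization, so comparisons within a labelled subgroup remain randomized ones, and misassignment is non-differential by arm among subjects randomized concurrently. One qualification concerns calendar time: the two lowest-dose arms closed with Amendment 4 (10 January 2022). The overstated share is 23% for consents from 16 July to 31 December 2021, against 84% for January to 24 April 2022. That shifts fractions of a subject per arm and does not alter the conclusion.

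**Conclusion.** The point holds as a small data-convention error. The stated rule exceeds completed age by one year for about half the subjects, given uniform birthdays and consents spread over the year. It would place roughly 1 to 4 of about 160 Part 1 subjects in 65-79 who are still 64, and a smaller share in the oldest category. Both counts depend on assumed age distributions.

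Anyone tempted to read this as a threat to the efficacy conclusions would go too far: the primary analysis is unaffected, the primary-endpoint subgroups are exploratory, and the secondary analyses are supportive. This is a minor correction at the lowest level of importance.

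**What to change.** In SAP 6.3.2, define age as completed years. Take it from the eCRF demographics age, or from full date of birth and consent date where the full date is held. Use that value for both the age summary and the age subgroups. Keep the year difference only as a stated fallback, flagged in the listing for each subject to whom it applies.

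Before adopting this, the sponsor should confirm how the eCRF age is filled. If only birth year exists, the SAP should say so and relabel the variable.

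The cost is a line or two of SAP text, a small programming change and no new data. There is a modest downside. The eCRF age refers to enrollment, which the documents do not clearly tie to main consent. If enrollment means randomization, the dates are about two weeks apart, and a birthday falls between them for about 14/365 = 4% of subjects, against about 50% affected by the present rule. A fallback also puts two definitions in one table, which is why it should be flagged.

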6.3.3 Medical History

Medical history will be coded using MedDRA version 24.0 or higher. Medical Histories will be summarized for the FAS using system organ class (SOC) and preferred term (PT) with frequencies and proportions of subjects experience each.

6.3.4 Prior Medication

Prior medications will be coded using the World Health Organization Drug Dictionary version B3 Global March 2021.

Prior medications are defined as any medications taken and stopped prior to the start of the study drug (including prior to placebo run-in period).

6.3.5 Exposure and Compliance

Exposure and compliance to MLS-101 or placebo will be summarized using the following parameters based on the data collected in the EDC:

- Treatment Duration, calculated as the number of days subject received randomized study drug: the date of last dose minus the date of the first randomized dose + 1.
- Total # of Capsules Taken (during the 8-week treatment period), calculated as total # of capsules dispensed minus total # of capsules returned
- Percent compliance (during the 8-week treatment period), calculated as:

$$\frac{\text{Total # of capsules dispensed} - \text{Total # of capsules returned}}{\text{Treatment Duration (days)} * \text{Planned # capsules/day}} \times 100$$

For Part 1, the planned number of capsules per day is 5/day. For Part 2, it is 1/day initially (dose: 100 mg QD). If a dose reduction occurs, 2 capsules/day will be taken (50 mg QD). If a second dose reduction occurs, then 1 capsule/day will be taken (25 mg QD).

If a bottle of capsules is not returned at any visit, such that the total number of capsules taken by that subject cannot be calculated, then the percent compliance for that subject will be set to missing.

The above parameters will be summarized for each treatment group and all active treatment groups pooled together.

The number and percentage of subjects with dose modification and the number and percentage of subjects with IMP withdrawal will be summarized for each visit by treatment group and pooled active treatment group.

A listing of the exposure and compliance parameters will also be provided, including reasons for modification, if they occur.

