#### **6.4. Study Drug Compliance**

Compliance with study drug will be assessed at each visit. Compliance will be assessed by direct questioning and counting returned tablets during the site visits and documented in the source documents and relevant case report form. Deviation(s) from the prescribed dosage regimen should be recorded.

A record of the quantity of study drug dispensed to and administered by each subject must be maintained and reconciled with study intervention and compliance records. Study drug start and stop dates, including dates for study drug delays and/or dose reductions will also be recorded.

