### 6.5.1. Hyperkalemia

If serum potassium level is elevated at the central laboratory measurement, the following actions are to be taken:

- Serum potassium > 5.2 and ≤ 5.5 mEq/L: Retest at local lab to confirm. If potassium remains elevated, reduce the MLS-101 dose according to [Table 3](#) (first dose-reduced level). Wait 2 to 7 days, then retest. If potassium remains elevated, reduce the MLS-101 dose again according to [Table 3](#) (second dose-reduced level).
- Serum potassium > 5.5 and ≤ 6 mEq/L: Retest at local lab to confirm. If potassium remains elevated, hold dose. Wait 2 to 7 days, then retest. If potassium ≤ 5.2 mEq/L, resume dosing. If potassium > 5.2 mEq/L, continue to hold dose. Wait 2 to 7 days, then retest. If potassium ≤ 5.2 mEq/L after second retest, restart at first dose-reduced level according to [Table 3](#). If potassium > 5.2 mEq/L after second retest discontinue study drug.
- Serum potassium > 6 mEq/L: Hold study drug dose and bring subject in for an unscheduled study visit for safety ECG and serum potassium retest at local lab; subject attends next regularly scheduled visit. If potassium from local lab retest ≤ 5.2 mEq/L, resume dosing. If potassium > 5.2 mEq/L, contact the sponsor's medical monitor for further guidance.

Note: If a retest of serum potassium level falls into a higher range than the original test, follow the instructions for the higher potassium range.

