4.1.3 Per Protocol Set (PPS)

The Per Protocol Set includes all subjects in the FAS who have completed the Study Week 8 visit without any major protocol violations that could influence the validity of the data for the primary efficacy evaluations. In the analyses based on PPS, subjects will be analyzed according to the randomized study treatment group. All criteria to exclude subjects from the PPS will be made based on a blinded review of the data prior to the unblinding of the study.

A subject may be excluded from the Per Protocol Analysis Set if any of the following criteria are met:

- Not meeting Inclusion/Exclusion criteria
- Use of prohibited medications. Subjects using rescue medications will not be excluded from the PPS unless subjects have met other criteria excluding them from the PPS
- Not compliant with the study drug
- Out of window efficacy assessment at study Week 8 visit

Alternate criteria for exclusion from the Per Protocol Analysis Set may be applied to accommodate unforeseen events that occurred during the conduct of the study.

Analyses on Per Protocol Analysis Set will be of supportive purpose and limited to primary endpoint (i.e., "product Estimand").

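### The SAP 6.3.5 compliance formula counts protocol-directed hold days as missed doses, because its two definitions of Treatment Duration disagree for subjects who hold and then resume

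*SAP*

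**What the plan says.** SAP 6.3.5 gives Treatment Duration two meanings in one bullet. In words it is "calculated as the number of days subject received randomized study drug"; as a derivation it is "the date of last dose minus the date of the first randomized dose + 1". Capsules taken are "calculated as total # of capsules dispensed minus total # of capsules returned". Percent compliance is capsules taken divided by Treatment Duration times the planned capsules per day. On the planned count: "For Part 1, the planned number of capsules per day is 5/day". In Part 2 the count is 1 per day at 100 mg QD, 2 per day after a first reduction and 1 per day after a second. No rule sets the count to zero while dosing is held.

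Protocol 6.5.1 directs holds. At a confirmed potassium above 5.5 and up to 6 mEq/L, dosing stops and the test is repeated after 2 to 7 days. Dosing resumes if the value has come down; otherwise, "If potassium > 5.2 mEq/L, continue to hold dose", with another 2 to 7 days before the next test. After that, dosing restarts at a reduced level or ends. Above 6 mEq/L there is also a hold, of unstated length, until a local retest.

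Protocol 6.4 requires study drug start and stop dates, "including dates for study drug delays and/or dose reductions will also be recorded". SAP 4.1.3 lists "Not compliant with the study drug" among the reasons for which a subject may be left out of the per-protocol set (PPS). It gives no percentage and does not refer to SAP 6.3.5.

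**The concern.** During a directed hold the subject is meant to take nothing. The unused capsules come back and reduce the numerator, while the calendar-span denominator still expects a full day's supply. A subject who followed the protocol exactly is scored as if doses had been skipped.

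Two outputs are exposed. The first is the compliance summary by treatment group and for the pooled active groups. Protocol 2.3 names hyperkalemia as a risk of aldosterone synthase inhibition, so holds should be commoner on active drug, and compliance there would be understated more than on placebo. The second is the PPS, if the blinded review uses this percentage to decide who was non-compliant.

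The same span also reports hold days as days on treatment in the exposure summary, contrary to the verbal definition.

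**Working it through.** The documents give no compliance result or threshold, so there is no stated figure to reproduce. The check applies the SAP formula to a subject who takes every dose that was not held.

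**Inputs**
- Span from first to last dose: D = 56 days (8 weeks of treatment, Protocol 4.1).
- Hold days: h = 2 to 7 for one interval and 4 to 14 for two (Protocol 6.5.1).
- Planned count: c = 5 per day in Part 1, 1 per day in Part 2 at 100 mg QD (SAP 6.3.5).
- Assumptions: the whole daily supply is held, held capsules are returned, and dosing resumes through day 56.

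**Formulas**
- As written: 100 × (56 − h) × c / (56 × c) = 100 × (56 − h) / 56. The count cancels when it is constant.
- With hold days removed: 100 × (56 − h) × c / ((56 − h) × c) = 100%.

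| Hold days | As written | Hold days removed |
|---|---|---|
| 2 | 54/56 = 96.4% | 100% |
| 4 | 52/56 = 92.9% | 100% |
| 7 | 49/56 = 87.5% | 100% |
| 14 | 42/56 = 75.0% | 100% |

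A shorter span magnifies the effect: a 7-day hold within 28 days gives 21/28 = 75.0%.

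**Part 2 after a two-interval hold.** Dosing restarts at the reduced level, so the planned count becomes 2 per day. For a hold on days 22 to 35, capsules taken are 21 × 1 + 21 × 2 = 63. Planned capsules, with the hold counted at 1 per day, are 21 + 14 + 42 = 77. That gives 63/77 = 81.8%, against 63/63 = 100% with the hold removed. The size shifts; the direction does not.

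**Would a subject fall below a cut-off?** The SAP states none, so a range is assumed. With a constant count, the score falls below the cut-off when h exceeds 56 × (1 − cut-off):
- 90%: h > 5.6, so 6 days
- 85%: h > 8.4, so 9 days
- 80%: h > 11.2, so 12 days
- 75%: h > 14.0, so 15 days

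At 80%, one interval of up to 7 days (87.5% or more) stays above the line. A 7-day hold with 10% of the remaining doses missed does not: 49 × 0.9 / 56 = 78.8%.

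**Who is unaffected.** If dosing never resumes, the last dose precedes the hold, no hold day enters the span and the score stays at 100%. Subjects above 5.2 and up to 5.5 mEq/L are directed to a dose reduction, not a hold.

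**Why the verbal definition alone is not a repair.** Read literally, it drops every day without drug. A subject who skipped 14 whole days by choice would score 42 × 5 / (42 × 5) = 100%. Only directed hold days should leave the denominator.

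**The case against.** The best reply is that measuring intake against the assigned regimen is a legitimate choice, with dose modifications reported separately, as SAP 6.3.5 does in a summary and in a listing with reasons. This does not settle the matter. In Part 2 the SAP changes the planned count after dose reductions, so it judges compliance against the regimen the subject was directed to take. Its verbal definition of duration also points away from the calendar span. Holds are the case left out.

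The remaining objections limit the consequence, and they stand. A reader might infer that subjects held for hyperkalemia will be classed as non-compliant and dropped from the PPS. The documents do not say so: SAP 4.1.3 has no percentage and no link to SAP 6.3.5, exclusion is optional and decided in blinded review, and the set is defined by major violations, which a hold ordered by the protocol is not. Equally, nothing in SAP 4.1.3 exempts such holds.

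A reader might also infer that any exclusion would be related to outcome, or try to state the share of an arm lost. Neither is supported. The trigger is potassium and the endpoint is systolic pressure, the documents give no relation between hold length and pressure change, and they give no hold frequency.

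**Conclusion.** The point holds as a derivation error with a small, bounded effect. For hold-and-resume subjects the formula understates compliance by 3.6 points (2 days) to 25.0 points (14 days, the longest two-interval hold in the band above 5.5 and up to 6 mEq/L). These figures assume a 56-day span, a constant planned count and no other missed doses. In Part 2 a two-interval hold changes the count, so the loss depends on timing.

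A larger understatement in active arms is likely from the drug's mechanism but is not quantified in the documents. An effect on the PPS is possible only, and it turns on an unstated cut-off. Even then it would touch a supportive analysis limited to the primary endpoint; the primary analysis uses the full analysis set and is unchanged.

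**What to change.** In SAP 6.3.5, give Treatment Duration one meaning. If the calendar span is kept for exposure, say so and drop the wording about days on which drug was received. For percent compliance, use a separate denominator: planned capsules summed over days, with zero planned on documented protocol-directed hold days. Days missed by the subject's own choice stay in.

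In SAP 4.1.3, state that such holds alone are not non-compliance for the PPS. Giving the numeric compliance limit there as well would let the blinded review apply the criterion consistently.

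The cost is one derivation line and one or two sentences of text. The delay dates are already to be recorded under Protocol 6.4, so no new data are needed and no dosing rule changes. The edit should be made before unblinding.
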